*****Note: if baby is awake, suggest doing video recording first after consent form***

CHECK FOR SPRINT SIGNAL

1. Check for Sprint signal with test device.
2. If there appears to be no signal or little signal, test a webpage (open Safari, go to gsu.edu)
3. If phone cannot get a signal, tell mom
 - a. *Unfortunately I cannot find a signal for the network the project phone is on, which means you would not be able to complete the program.*
 - b. *Thank you for your time and I am sorry you are not eligible at this time.*
4. Return to office and update Access database and matriculation table to indicate mom was ineligible due to lack of Sprint signal.

REVIEW CONSENT FORM

1. Take out 2 copies of the consent form and give one to mom
2. Go over each section – you don't have to read word for word but say the main points of each section.
3. Ask mom what questions she has after each section.
4. Have mom complete lines *Print Participant's Name, Child's Name, Participant's Signature, Date*
5. Assessor signs as *Researcher Obtaining Consent and Date*

CONDUCT ASSESSMENT

1. Go to Qualtrics Pre-Assessment on iPad (Qualtrics folder -> MBN part1)
2. Enter the ID #, mom's Initial, Assessor's name and date before mom starts with the questionnaire.
3. Provide mom with the iPad and explain to her how to use the iPad.
4. Sit next to mom if possible, so you can read the questions and/or instructions to her.
5. Help create comfort for moms to opt to have the questions read to them.
 - a. *Some moms prefer to have the questions read to them so that they can relax for a moment and think about the answer without having to read and enter responses. Other moms really prefer reading on their own.*
 - b. *Either way we will start the questions together and go over instructions for each section together. The questionnaires are divided into sections, which are separated by pictures. When we get to those pictures we will stop so that I can review the instructions for each new section with you. Sometimes questions are asked in a way that might be unfamiliar or they might be confusing. At any point that you have a question about what something means, please let me know so that I can address your question. Also, if I notice that you are coming up to a section with items that moms sometimes find confusing, I'll let you know so that we can talk about those and I can explain them up front.*

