 - *What I'm interested in seeing are things that you and your baby are both comfortable with and used to, and things that your baby loves to do.*
 - *Please feel free to move around as is comfortable for you and your baby. You don't have to sit in one place, but I'll need to know what room you'd like to be in so that I can move along with you.*
 - *Attend to any needs your baby might have during this time just as you normally would.*
- **Note:** The purpose of this activity is to encourage the caregiver and child to engage in whatever activity they enjoy and to be as non-restrictive as possible. It is important not to impose any structure on the caregiver above and beyond the instructions. Therefore, do not restrict the caregiver's and child's movement by asking them to stay in one place.
 - *After these 5 minutes, I will give you the instructions for the second part of the recording which lasts 5 minutes. What questions do you have?*
 - **Begin the first 5 minute interaction**

- Record header: *"This is a Mom & Baby Net interaction with family ID # _____; the mother's initials are _____."*
- Tell the participant that we are now beginning the interaction. *You can begin now.*
- After 5 minutes, stop recording and say *Okay, you have finished the first interaction.*

2. **SECOND INTERACTION (5 Minute Looking at Books): Instructions**

- **Place the books near mom and baby so mom can see/reach them:**
1)Brown Bear; 2) Touch and Feel Puppy; 3)Touch and Feel Farm
- Record giving instructions to mom then stop before beginning interaction recording
- Instructions:
 - *During the next five minutes, you and your baby can spend a little time with these books.*
 - *However you want to use the books with your baby is fine.*
 - *Feel free to attend to whatever needs your baby might have.*
 - *What questions do you have?*
- **Record the second interaction**
 - i. Record header: *"This is a Mom & Baby Net interaction with family ID # _____; the mother's initials are _____."*
 - ii. Tell the participant she can begin. *You can begin now.*
 - iii. After 5 minutes, stop recording and say *Thank you! You have finished the video recording piece of the visit.*
 - iv. *Collect 3 assessment books then give 2 participant board books to leave with family.*

BEFORE LEAVING THE HOME

1. Complete iPhone Customization Form
2. Review the **Data Checklist** to ensure all steps and documentation are complete.
 - a. Sprint signal
 - b. Qualtrics Questionnaire, ASRI

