7. AFTER THE INITIAL RECRUITMENT CALL

[figure not shown]
- Update Access Database - Tracking Information Form
 - Update/confirm contact, alternate contact, and demographic information
 - Enter phone screen information
 - Enter eligibility information
 - Enter Call Attempt information and enter Call Back Date if needed to call back to schedule preassessment

- If applicable, enter Scheduled Appointments information

Scheduled Appointments						
Mom ID	Type	Date	Appointment Details			Check the Completed Assessments Q1 Q2 Interactions iPhoneTrain Notes
			Time	Assessor	Status	

- Update Matriculation Table
 - Entire 'Screening' section
 - 'PreAssessment Scheduled' column of 'PreAssessment' section (if scheduled)

- Update Google calendar
 - Add scheduled preassessment on Assessment Visit calendar
 - Add assessor as 'guest' when known

Preassessment ID ###

Mar 21, 2018 10:00am to 12:00pm Mar 21, 2018 TIME ZONE

All day Does not repeat

EVENT DETAILS FIND A TIME

Add location

Add conferencing

ADD NOTIFICATION

Assessment Visit

Busy Default visibility

Add description

[contact]

GUESTS

Gucata can:

Modify event

Invite others

See guest list

Mom & Baby Net Remote Assessment & Training Procedures

Schedule Consent Call (10 minutes) [PROJECT COORDINATOR]

1. Explain changes in procedures (moms on wait list)
 - a. *Hi! This is [name] with the Mom & Baby Net project. Do you have about 10 minutes to talk? I was calling to let you know that we have a spot open for you in the project but our procedures will be a little different since we cannot do home visits right now. Are you still interested in participating and hearing what the next steps will be?*
 - i. If no: *I'm sorry to hear that. Can I ask why you are no longer interested?* If mom is too overwhelmed right now, offer to leave her on the waitlist and check back again when the next spots are open.
 - ii. If yes: continue with script
 - b. *Great! If you remember, the usual next step would have been to do the first home visit, but due to coronavirus, we are not doing home visits. Instead, we will do everything via phone or video call. We will walk you through each step along the way. After this call, you will be in touch with your coach, who you will be working with you for the rest of the program.*
2. Explain sending consent and iPhone agreement

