 3. *What I'm interested in seeing are things that you and your baby are both comfortable with and used to, and things that your baby loves to do.*
 4. *Please feel free to move around as is comfortable for you and your baby but make sure that both you and your baby are visible on the screen at all times.*
 5. *Attend to any needs your baby might have during this time just as you normally would.*
 6. *After these 5 minutes, I will stop recording then I will give you the instructions for the second part of the recording which lasts 5 minutes. What questions do you have?*

7. Answer any questions mom has.
8. Stop recording on Zoom.

- ii. Record Free Play Video
 1. Give mom time to finish setting up for the video and confirm that she is ready.
 2. Coach should record using Speaker View and have the running time visible (or use a timer on your phone) set to make sure you get a minimum of 5:30 minutes of recording.
 3. *I am going to start recording, say an intro sentence for the video, then ask you to begin.*
 4. Select 'record' on Zoom
 5. *This is an interaction video with participant [say ID #], the mother's initials are [say mom's initials]*
 6. To mom: *You can begin now.* Coach – mute your microphone to mute your own background noise.
 7. After 5:30 minutes, stop recording on Zoom, unmute yourself, and say *Ok, the first video is finished.* Allow the mom to transition. *Now we will do the second video.*

- d. Books video (use Color and Animal baby books given to all moms)
 - i. Record Book video instructions
 1. Select record on Zoom
 2. *During the next five minutes, you and your baby can spend a little time with these books.*
 3. *However you want to use the books with your baby is fine.*
 4. *Feel free to attend to whatever needs your baby might have.*
 5. *What questions do you have?*
 6. Answer any questions mom has.
 7. Stop recording on Zoom.
 - ii. Record Books Video
 1. Give mom time to finish setting up for the video and confirm that she is ready.
 2. Coach should record using Speaker View and have the running time visible (or use a timer on your phone) set to make sure you get a minimum of 5:30 minutes of recording.
 3. *I am going to start recording, say an intro sentence for the video, then tell you to begin.*
 4. Select 'record' on Zoom
 5. *This is an interaction video with participant [say ID #], the mother's initials are [say mom's initials]*

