- b. For moms in PALS condition only: When you get to setting mood anchor page, have mom pause zoom by returning to home screen, and advancing until she reaches page shown on screen. You will talk to mom about setting mood anchors as she does it on her device; She will then follow along with audio for the next couple of pages as she practices rating her mood.

8. For moms in the PALS condition who using Zoom on a device other than project iPhone

- a. Have moms set phone she is using on Zoom on tripod, and have her go through the pages on her project phone, as coach screen shares. Mom will be able to see both coach and video as she follows along
- b. For mom in PALS condition only: ask mom to show you her page when setting mood anchors and rating mood
- c. Review pages via screen sharing as you normally do during training visit and answer questions mom has about different pages in section menu of app.

Before ending the call

1. Schedule your Session 1 Zoom call with mom and show her how to use the calendar not only for reminding her of weekly Zoom calls, but for doctor's appointments or anything else she needs to schedule.
 - a. Have her enter your scheduled Zoom call and use a reminder.

- b. It is suggested that when you add coach appointments to your calendar that you include a 'day before' reminder as well as a 15-minute reminder and send an Invite. It would be great if moms have a regular time that can be set up to 'Repeat Weekly', but if not, you could send week to week.
- 2. Ask if there are any updates to her alternate contact info (at least 3); Confirm best means of contact for mom

After App Training Call

- 1. Update Access
 - a. Update scheduled appointments form
 - i. Change 'scheduled' to 'complete'
 - b. If needed, update contact information
- 2. Update Matriculation table
 - a. Training tab: Mark training visit completed (Y)

<>REMOTE POST ASSESSMENT PROCEDURES<>

Schedule Post Assessment

- 1. Coach will schedule post-assessment with mom during session 14 (or last) Coach Call as usual
 - a. *Typically, we would do the last visit in the home, but due to the coronavirus we will complete post assessments using Zoom as we did for our coach calls. Just as we did at the pre-assessment, you'll complete some questionnaires and we will make 2 videos of you and your baby. To get ready for our Post-Assessment Zoom Call, I'd like to get a little information from you.*

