 17. After 5:30 minutes, stop recording on Zoom, unmute yourself, and say *Ok, the second video is finished.*
- e. Reset Zoom
 - i. *Great job on the videos! Now we can continue to the surveys. So we don't run out of time, I am going to end this call and we are going to get right back on this same Zoom to continue.*
 - ii. End Zoom call then start again immediately.
 - iii. Ask mom if she needs to take care of any needs for the baby or if she is able to put the baby down or give to another adult so she can focus on the surveys.

5. Questionnaires
 - a. Post Assessment Questionnaire Part 1 (labeled as part 2 in Qualtrics: T2_part2)
 - i. *Now we will begin the questionnaires. They are split into two parts, so we don't have to complete both today. They are very similar to the questionnaires you completed at your very first home visit. Each part will take 30-40 minutes to*

complete. We can start Part 1 and see how far we get. If we need to, we can complete the rest of the survey on our next scheduled call.

- ii. I am now sending you a link to the first survey we will complete. Please let me know when you have received it and you can go ahead and click on it.*
- iii. Send link to T2_Part 2 survey to mom
 1. Link: (see links document)
 2. If mom is doing surveys on their phone, text survey link to mom's project phone
 3. If mom is using laptop, email survey link
 4. If mom is restarting a partially finished survey, see steps below to get link to that survey and start where she left off
- iv. Coach will have PDF of survey open to look at (printed or on computer). If mom needs to stop before reaching the end of this survey, make a note on the PDF of where she ended.
- v. Set up surveys
 1. If mom is using their project phone: *When you click on the link, we will stay on Zoom. Even though we won't be looking right at each other through video, I will walk you through everything.*
 2. If mom is using own laptop/table: *If you want to set your phone up somewhere during these surveys, we will not necessarily need to see each other, but I will be walking you through each section of the survey.*
- vi. Coach will instruct mom how to fill out the first page of info: ID #, mom initials, assessor name, date (mm/dd/yyyy)
- vii. Read instructions for each section
 1. Coach will read through introductory instructions and instructions for first section.

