Statistical Analysis Plan

Title: Reducing Maternal Depression and Promoting Infant Social-Emotional Health & Development

NCT03464630

Date: 09/18/2016

Analytic Strategy

Constructs. We will use a systematic approach to construct development to create two parent outcomes (mother positive/negative) and one infant outcome (infant social emotional functioning). *For our outcomes of maternal depression, parenting knowledge and stress, we will examine single indicants. To view potential intervention moderating effects, we will attempt to create a maternal contextual risk indicant (e.g., isolation/support, relationship status, conflict, economic hardship); for maternal depression prior to intervention as a potential moderator, we will view depression onset, chronicity, and severity as well as presence of other treatment including medication to examine each of these and their effect on intervention outcomes.* For factor analysis, given appropriate internal consistency and inter-rate reliability, we will examine questionnaire scales and observational codes using factor analytic techniques [99], retaining a 5:1 subject to parameter ratio. Scale factor loadings above .30 and communality estimates above .15 will be confirmed within SEM methodology to produce fit indices to view how each indicant set fits into their specified domain. If satisfactory, unit-weighting of the standardized score for each indicant will be summed. If not, we will select an index variable within each domain to represent the outcome.

Random Sampling/Attrition Analysis. Though mother-infant pairs will be randomly assigned to the intervention, condition differences may exist due to random sampling failures or differential attrition. To address this issue, 2×2 (Group x Attrition Status) MANOVAS will be performed using the baseline assessment for mother, infant and contextual risk variables. The presence of a statistically significant Group main effect would provide evidence that random assignment was not effective in equating groups. A second possible source of nonequivalence is differential attrition by condition. A Group x Attrition Status significant interaction provides evidence of differential attrition between groups. In general, analyses will proceed using an “intent to treat” approach and all participants recruited will be included in subsequent analyses.

Examination of Acute Intervention Effects (Aim 2)

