(Aims 2.1 - 2.3) Our post-assessment n, to examine acute intervention effects, is expected to be 150 (75/condition). We will initially view intervention effects on our mother/infant outcomes using a 2 (pre-post) $\times 2$ (MBN intervention group) repeated measure analysis of variance. We will examine the inter-correlations among outcomes and, if significant, will use a MANOVA approach to examining MBN intervention effects. The F test is robust to non-normality if such non-normality is caused by skewness rather than outliers. We will take appropriate measures to reduce outlier influences. **(Aim 2.4)** To examine the relations between mother change (parenting and maternal depression) and infant change, one approach will be to create individual beta estimates for mothers and infant utilizing the polynomial contrast function within MANOVA to produce individual trajectory scores reflecting parent and infant change from pre to post that can then be used in external between-condition covariate analysis. The trajectory scores will be subjected to an analysis of covariance with infant change trajectories as the dependent variable and parent change as the covariate. We will determine whether the parent change covariate is significantly related to the dependent variable (demonstrating that changes in parenting behavior and child functioning covary). We will determine the statistical significance and effect sizes of intervention effects (ignoring the covariate). We will then determine if entering the parent functioning covariate modifies the intervention effect size and statistical significance. If parent change is strongly linked to infant change, then entering the covariate should result in nonsignificant intervention effects. Estimates of covariance-adjusted effect sizes will provide estimates of the proportion of intervention effect size that can be explained by the parenting change variable. We will test for between-group heterogeneity of covariance to determine whether the strength of association between change in parenting and infant functioning differs by intervention group.

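### The Aim 2 models have no term for assessment mode, although the later remote procedures moved some dyads from home to Zoom between pre and post; adding one costs little and gains about 0–5 points of power

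*SAP*

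**What the plan says.** The SAP carries "Date: 09/18/2016". Its section on acute intervention effects says "We will initially view intervention effects on our mother/infant outcomes using a 2 (pre-post"; the other factor is intervention group. Aim 2.4 regresses infant change on group with parent change as the only covariate. Nothing in the SAP gives a term, stratum or sensitivity analysis for how an assessment was carried out.

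Section VI of the protocol (COVID Remote Procedures) came later. It tells waitlisted mothers that "due to coronavirus, we are not doing home visits". Its post-assessment part says "Typically, we would do the last visit in the home, but due to the coronavirus we will complete post assessments using Zoom" and introduces the surveys with "They are very similar to the questionnaires you completed at your very first home visit". It also describes dyads who are remote at both points.

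Measurement conditions differ by mode:

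- **Movement.** For home free play, Section II says "It is important not to impose any structure on the caregiver above and beyond the instructions", and the assessor follows with the camera. Remotely the mother is told to "make sure that both you and your baby are visible on the screen at all times".
- **Books.** Home visits use three named assessment books, collected afterwards. Remote pre-assessment uses two supplied books; remote post-assessment uses those or suitable ones the mother owns.
- **Administrator.** An assessor runs the home visit. The assigned coach runs the remote calls, and one post survey has an arm-specific version.
- **Questionnaires.** Both modes use Qualtrics. At home the assessor is to "Help create comfort for moms to opt to have the questions read to them", and part 1 comes first. Remotely the mother completes them by link with the coach on Zoom, and the Qualtrics part 2 survey, which holds the PHQ, comes first.

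**The concern.** A dyad seen at home before and on Zoom after changes measurement conditions in the middle of its own change score. A dyad with one mode throughout largely does not. Any shift due to mode is therefore part of the change score for some dyads only, and a model with time and group alone cannot separate it out.

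Three things follow. In the group-by-time test, the shift is extra variance, and a chance imbalance in switchers between arms stays uncorrected. In the pre-post main effect it is bias, because every switcher moves the same way in time. In Aim 2.4, a switch acts on mother and infant together, so it can make their changes covary for a reason unrelated to treatment.

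**Working it through.** **Inputs.** From the SAP power analysis: 75 per condition, alpha .05, pre-post correlation r = .21 or .68. The documents do not give the share of dyads that switched (p) or the shift in their change (m, in SD of change). I assume p = .10–.50 and m = .3–.8.

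**1. The plan's own figures.** For group by time with N = 150 and two waves, use noncentral F(1,148) with λ = f²·N·2/(1−r) and d = 2f. The detectable d is .289 (r = .21) and .184 (r = .68) at 80% power, and .372 and .237 at 95%. The SAP states .29, .18, .37 and .23. Power at those values is .802, .782, .948 and .938, so the figures reproduce within two points. They contain no allowance for mode.

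The SD of change is √(2(1−r)) = 1.257 or .800. The between-arm difference in change at 80% power is 4f = .579 or .368, which is .46 SD of change in both cases (.4605 unrounded). The noncentrality is .4605 × √(75/2) = 2.820.

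**2. Group by time.** Switching raises the variance of change from 1 to 1 + q, where q = p(1−p)m². Variance explained is q/(1+q), and the equivalent in extra dyads is 150q. Unadjusted power ≈ Φ(2.820/√(1+q) − 1.976). A three-level factor costs about 2/146 = 1.4% of variance, so adjusted power ≈ Φ(2.820/√1.014 − 1.976) = .795.

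| p | m | q | explained | extra dyads | unadjusted | adjusted |
|---|---|---|---|---|---|---|
| .10 | .3 | .0081 | 0.8% | 1.2 | .797 | .795 |
| .20 | .3 | .0144 | 1.4% | 2.2 | .795 | .795 |
| .10 | .5 | .0225 | 2.2% | 3.4 | .792 | .795 |
| .30 | .5 | .0525 | 5.0% | 7.9 | .780 | .795 |
| .20 | .8 | .1024 | 9.3% | 15.4 | .761 | .795 |
| .50 | .8 | .1600 | 13.8% | 24.0 | .740 | .795 |

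Simulation at N = 150 agrees. Unadjusted against adjusted power was .791 and .791 (p = .10, m = .5), .791 and .790 (.20, .3), .775 and .788 (.30, .5), and .745 and .795 (.50, .8). The net gain is about 0–5 points.

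**3. Chance imbalance.** The protocol describes 1:1 allocation by random number generator and mentions no blocks or strata. At p = .25 the SE of the arm difference in switching is √(2 × .25 × .75/75) = .071. A gap of 10 points or more has z = .10/.071 = 1.41, and so occurs about 16% of the time.

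Given a 10-point gap (.30 against .20) and m = .5, the group-by-time estimate is off by .10 × .5 = .05 SD of change. Its SE is √((1.0525 + 1.04)/75) = .167, and .05/.167 = .30. The rejection rate under no effect is then 1 − Φ(1.66) + Φ(−2.26) ≈ .060. Averaged over all randomisations it remains .05.

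**4. Pre-post main effect.** The bias is p × m: from .10 × .3 = .03 to .50 × .8 = .40 SD of change.

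**5. Aim 2.4.** If a switch shifts parent and infant change by the same m in the same direction, and they are otherwise unrelated, their correlation becomes q/(1+q). That is .05 at p = .30, m = .5, and .008 to .138 over the assumed range.

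**The case against.** The best case against has four parts.

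- **Size.** Neither p nor m has a source. Only dyads in the programme when home visits stopped can have switched. The programme is 14 weekly sessions. If enrolment ran evenly over 24–36 months and time in programme was 3.5–5 months (both assumed), the share is 3.5/36 = 10% to 5/24 = 21%. At 20% the gain runs from nil (m = .3) to about 3 points (m = .8). This stands: the upper half of the assumed range for p is less plausible than the lower half, and at the low end the two degrees of freedom cancel the gain.
- **Self-report.** Questionnaires stay on Qualtrics, mothers could also self-complete at home, and section instructions are still read to them remotely. This stands in part. The helper, device and order of parts do change, but a material effect on self-reported outcomes is not shown.
- **Same-mode dyads also change.** Remote-only dyads may use different books at post-assessment. True, so the pattern factor captures most but not all of the change in conditions.
- **The arm-related problem lies elsewhere.** Remote assessments are run by the assigned coach, who uses an arm-specific post survey link. A mode term does not correct bias that differs by arm. This stands and limits what the fix can claim.

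A reader might also see a scoring fault in stopping at 5:00 at home and 5:30 remotely. The documents do not support that. Mothers are told five minutes in both modes, the remote recording includes a spoken header, and the coding rules are not given, so a fixed segment may already be scored.

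**Conclusion.** The omission is real and its consequence modest. The SAP predates the remote procedures, and no Aim 2 model allows for the mixture of assessment patterns that those procedures created. The filmed codes are the clearest case. Under the assumed 10%–50% switching and .3–.8 SD shift, adjusting gains about 0–5 points of power. It also corrects any realised imbalance between arms and removes a possible source of spurious covariance in Aim 2.4.

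Two stronger readings are tempting. One is that the treatment effect is biased. The documents do not show this: with 1:1 randomisation, switching is balanced between arms in expectation, so the group-by-time test keeps its level overall. The systematic bias falls on the pre-post main effect, which is not the treatment contrast. The other is that every outcome is materially distorted. Every outcome is exposed, but only in dyads that switched, and the documents give neither their number nor the size of any shift.

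**What to change.** Add a three-level assessment-pattern factor (home-home, home-remote, remote-remote) to each Aim 2 model, including Aim 2.4. Define it by planned pattern: the randomisation date, and that date plus the scheduled programme length, each set against the date home visits stopped. It is then fixed at randomisation. Actual mode at each wave should not be the adjustment variable. It depends on time in programme after randomisation, and mothers may stop early and go to post-assessment.

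Tabulate actual pattern by arm. As sensitivity analyses, add pattern by group, and repeat Aim 2 in dyads with the same mode at both points.

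The cost is SAP wording, two degrees of freedom, and a planned post date that has to be constructed, since the Access appointment records described hold scheduled and completed visits only. A few dyads near the stop date will have an actual pattern that differs from the planned one; the tabulation will show how many. The report should say that the factor does not address remote assessment by a coach who knows the arm.
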